# 7. ENDPOINTS AND COVARIATES

## 7.1. Efficacy Endpoint(s)

Objective tumor response, as assessed using the Response Evaluation Criteria in Solid Tumor (RECIST) version 1.1 by calculating the Overall Response Rate (ORR), Progression Free Survival (PFS), and Overall Survival (OS).

All efficacy endpoints are secondary in this study, which include objective tumor response, progression-free survival (PFS), and overall survival (OS) for each tumor type in the expansion cohorts. The above efficacy endpoints are derived based on the disease response per investigator evaluation on the CRF pages, which is the primary method of documentation of disease.

- **Overall Response (OR)** – or Response Rate (RR) is defined as complete response (CR) or partial response (PR) according to RECIST 1.1 ([Appendix 2](#)). Overall response is the best response recorded from first dose until disease progression/recurrence.
- **Progression Free Survival (PFS)** - is defined as the time from Cycle 1 Day 1 (C1D1) to first documentation of disease progression or to death due to any cause, whichever occurs first. Subjects last known to be 1) alive 2) on treatment or within the post-treatment follow-up period and 3) progression-free, are censored at the date of the last disease assessment that verified lack of disease progression. Subjects who start new anti-cancer treatment prior to the end of post-treatment follow-up period and have adequate baseline and on-treatment objective disease assessments without evidence of progressive disease are censored at the date of the last objective disease assessment. Subjects with inadequate baseline or no on-study disease assessments are censored at C1D1 unless death occurred prior to the first planned assessment (in which case the death is an event). Subjects with at least one on-study disease assessment who discontinue treatment without disease progression and without death within 28 days of discontinuation are censored at the date of the last objective disease assessment that verified lack of disease progression (if progression or death is within 28 days of discontinuation the progression or death is an event). Subjects with documentation of progression or death after an unacceptably long interval (>16 weeks) since the previous disease assessment will be censored at the time of the previous assessment.

PFS (days) = [progression/death date – C1D1 + 1].

- **Overall survival (OS)** is defined as the time from initial dose until death from any cause, and is measured in the intent-to-treat population.

More details of censoring are provided in [Appendix 3](#).

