##### Part 2 (Expansion) Primary Objective

- To confirm safety and tolerability and explore preliminary evidence of anti-tumor activity of PF-06647263 based on response rate (RR) at the RP2D in patients with previously treated metastatic TNBC and advanced platinum-resistant OVCA which express EFNA4.

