### Primary Endpoint (Part 2)

- Response rate (RR) as determined by the Response Evaluation Criteria in Solid Tumor (RECIST) version 1.1 criteria.

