### Secondary Endpoints (Parts 1 and 2)

- Adverse Events as characterized by type, frequency, severity (as graded by NCI CTCAE v.4.03), timing, seriousness and relationship to study therapy;
- Laboratory abnormalities as characterized by type, frequency, severity (as graded by NCI CTCAE v.4.03) and timing;
- Vital Sign abnormalities;
- Systemic PK exposure of PF-06647263, total antibody, and unconjugated payload will be determined with validated methods. Standard noncompartmental PK parameters will be determined from the respective concentration-time data;

- Immunogenicity of PF-06647263; Human serum ADA (anti-PF-06647263 antibody) samples will be analyzed for the presence or absence of anti-PF-06647263 antibodies, following a tiered approach using screening, confirmation and titer/quantitation;
- Objective tumor response, as assessed using RECIST version 1.1 by calculating the Overall Response Rate (ORR), Clinical Benefit Response Rate (CBRR), Progression Free Survival (PFS), and Overall Survival (OS)-Part 2 only.

CCI [REDACTED]

[REDACTED]

[REDACTED]

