### **9.2. Statistical Analyses**

#### **9.2.1. Primary Analysis**

Dose Limiting Toxicity (DLT) is the primary endpoint of the dose escalation component of the study, which will be summarized by dose level using the Per Protocol Analysis Set for patients in the dose escalation portion of the study. A listing of the DLTs will also be provided.

If necessary, a summary and listing of the DLT by malignancy may be provided using the Per Protocol Analysis Set for patients in the MTD expansion portion of the study.

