#### **9.2.2. Secondary Analyses**

##### **9.2.2.1. Efficacy Analysis**

In this Phase 1 study efficacy is a secondary objective. Note that the efficacy analysis is to be conducted by malignancy for patients in the MTD expansion cohorts who are in the Safety Analysis Set and have baseline disease assessment and at least one post-baseline disease assessment. In the event that a large number of patients in the escalation portion of the study have the same malignancy, the efficacy analysis may be conducted.

Summary tables of best Overall Response Rate, Progression Free Survival, and Overall Survival will be provided overall and by malignancy. Efficacy listings will be provided that include best response, first CR/PR date, last date with CR or PR, most recent date without progression, progression date, death date, date of first response and last tumor assessment date, etc.

A response rate overall for Part 1 dose escalation and response rates by low, medium, and high dose groups may be presented.

The following table provides an overview of the efficacy analysis.

Endpoint	Analysis Set	Statistical Method	Model/ Covariates/ Strata	Missing Data	Interpretation
Overall response	Per Protocol, expansion cohorts, etc.	Exact CI	By dose range/ malignancy	Censored per Section 11.3	Secondary Analysis
Progression Free Survival (PFS)	Per Protocol, expansion cohorts	Kaplan-Meier	By malignancy	Censored per Section 11.3	Secondary Analysis
Time to Progression (TTP)	Per Protocol, expansion cohorts	Kaplan-Meier	By malignancy	Censored per Section 11.3	Secondary Analysis
Duration of Response (DR)	Per Protocol, expansion cohorts	Kaplan-Meier	By malignancy	Censored per Section 11.3	Secondary Analysis

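### The SAP gives Part 2 response rate conflicting status and, separately, two denominators that both leave out treated patients with no post-baseline scan

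*SAP*

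**What the plan says.** **Status of RR.** In SAP Section 2.4, the Part 2 primary objective includes the aim to "explore preliminary evidence of anti-tumor activity of PF-06647263 based on response rate (RR) at the RP2D", and the entry under the Part 2 primary endpoint is "Response rate (RR) as determined by the Response Evaluation Criteria in Solid Tumor (RECIST) version 1.1 criteria". The secondary endpoints for Parts 1 and 2, in the same section, include "Objective tumor response, as assessed using RECIST version 1.1 by calculating the Overall Response Rate (ORR" and further measures. Section 7.1 says "All efficacy endpoints are secondary in this study", names objective tumor response among them, and applies this to each tumor type in the expansion cohorts. Section 9.2.1, the primary analysis, says "Dose Limiting Toxicity (DLT) is the primary endpoint of the dose escalation component of the study"; its only Part 2 content is an optional DLT summary. Section 9.2.2.1 opens with "In this Phase 1 study efficacy is a secondary objective", and its overview table marks the overall response row as a secondary analysis.

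**Denominator of RR.** The text of Section 9.2.2.1 takes expansion-cohort patients from the Safety Analysis Set who have a baseline and at least one post-baseline disease assessment. The table below it names the Per Protocol set and the expansion cohorts, and ends the list with an et cetera. Its missing-data column refers the response row to the censoring rules of Section 11.3.

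**Method.** Section 9.1 gives binary endpoints an exact two-sided 95% interval. Section 4.1 states that there are no hypotheses and that the emphasis is on estimation.

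**The concern.** There are two separate problems.

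The first is the status of RR. A reader of Section 2.4 expects RR to be the main Part 2 result. A reader of Sections 7.1, 9.2.1 and 9.2.2.1 would report it as secondary and find no RR entry in the primary analysis.

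The second is the denominator. Two sets are named for one estimate and the list in the table is left open, so the set could be settled after the data are seen, in an open-label study with investigator-assessed response. Both named sets also omit treated patients with no post-baseline scan, among them any who die or deteriorate first. In a study that tests nothing, the point estimate and its interval are the whole efficacy result, and in cohorts of 15 a few omitted patients move that estimate visibly.

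**Working it through.** **1. Can the statements on status be read together?**

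- Section 7.1 treats overall response and response rate as the same quantity, so ORR in the secondary list and RR as primary endpoint are one endpoint under two names.
- The sentence in 7.1 cannot be limited to Part 1, because it refers to the expansion cohorts.
- The secondary list in 2.4 is headed for both parts and ends with a Part 2 only tag. Whether that tag covers only the last item or the whole list, ORR in Part 2 is still included.
- Section 9.2.1 gives RR no place in either part.

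No reading makes RR consistently primary or consistently secondary in Part 2. Section 1 records no amendments, so all of this is current text.

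**2. What do the two sets have in common, and where do they differ?**

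| Set for RR | Post-baseline assessment required | Major Cycle 1 deviations removed |
|---|---|---|
| Text of 9.2.2.1 (Safety set with assessments) | Yes | No |
| Table of 9.2.2.1 (Per Protocol, Section 6.2) | Yes | Yes |

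The mITT set in Section 6.6.1 would keep patients who progress or die before the first tumor assessment. It is optional, is meant for interim and conference use, and is not assigned to RR. Neither is the Full Analysis Set.

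Section 11.3 covers PFS, duration of response and time to progression. A yes/no response cannot be censored, so the cross-reference gives no rule for patients without an evaluable response. For PFS, the same appendix counts death before the first planned assessment as an event.

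**3. Direction of the effect.** Let x be the responders among n treated patients, and k the number with no post-baseline assessment. None of those k can be a responder, so the rate goes from x/n to x/(n − k). This is larger than x/n when x > 0 and k > 0, and stays at zero when x = 0.

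**4. Size.** The plan's own figure is reproduced first: 15 TNBC + 15 OVCA = 30, as in Section 5. That number rests on clinical considerations, with no power or response threshold behind it, so there is nothing further to reproduce.

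For the intervals, the exact method is taken to be Clopper-Pearson: lower limit = 2.5% quantile of Beta(x, n − x + 1), upper limit = 97.5% quantile of Beta(x + 1, n − x). Responder and exclusion counts are assumed, for a cohort of 15:

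| Responders | Unscanned patients dropped | RR | Exact 95% CI |
|---|---|---|---|
| 3 | 0 | 3/15 = 20.0% | 4.3 to 48.1% |
| 3 | 2 | 3/13 = 23.1% | 5.0 to 53.8% |
| 3 | 3 | 3/12 = 25.0% | 5.5 to 57.2% |
| 3 | 5 | 3/10 = 30.0% | 6.7 to 65.2% |
| 0 | 0 | 0/15 = 0% | 0 to 21.8% |
| 0 | 3 | 0/12 = 0% | 0 to 26.5% |
| 0 | 5 | 0/10 = 0% | 0 to 30.8% |

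With three responders, dropping three patients adds 25.0 − 20.0 = 5.0 percentage points, and dropping five adds 30.0 − 20.0 = 10.0.

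**5. Gap between the two sets that the plan names.** Suppose all 15 are scanned, 3 respond, and Per Protocol removes one patient for a major deviation. If that patient is a non-responder, RR moves from 3/15 = 20.0% to 3/14 = 21.4% (4.7 to 50.8%). If that patient is a responder, it moves to 2/14 = 14.3% (1.8 to 42.8%). This exclusion can therefore act in either direction.

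**The case against.** The case against giving this much weight is substantial, and most of it stands.

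- A reader might infer that Part 2 RR has no analysis. It has one: Sections 9.1 and 9.2.2.1 together give an exact 95% interval by malignancy. What is missing is an RR analysis designated primary.
- A reader might infer that the secondary label affects error rates or a decision. It does not: the plan has no hypothesis, no formal test and no response threshold.
- A reader might infer that the unsettled denominator follows from the label. It does not: it comes from text and table disagreeing within 9.2.2.1, and would remain if every label agreed.
- A reader might infer that every exclusion raises RR. Step 5 shows that the deviation exclusion need not. Only dropping patients without a post-baseline scan has a fixed direction.
- The two named sets share the assessment requirement and differ essentially in Cycle 1 deviations. The et cetera may refer to Part 1 dose groups, since only that table row mentions dose range. That is possible, but the row does not say so.
- The move from 20.0% to 25.0% rests on assumed counts and compares all treated patients, a set the plan does not assign to RR, with scanned patients. The intervals overlap almost entirely.
- Section 2.4 is inconsistent within itself and the protocol is not at hand, so the SAP alone cannot prove which status was intended.

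These points limit the consequence. They do not remove the contradiction, the two sets, or the missing rule for unscanned patients.

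**Conclusion.** The point holds as two separate defects. The status of Part 2 RR is contradictory across Sections 2.4, 7.1, 9.2.1 and 9.2.2.1. Independently, 9.2.2.1 names two denominators that both omit treated patients without a post-baseline assessment, and it refers to censoring rules that cannot apply to a binary endpoint.

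What is at stake is the headline estimate. In a cohort of 15 with three responders, leaving out three to five unscanned patients raises RR by 5 to 10 percentage points. Those counts are assumptions, because the plan gives no expected number of unscanned patients; if there are none, this shift is zero. The direction for unscanned patients does not depend on the counts. This should be corrected, but it does not invalidate the design.

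**What to change.** **Status.** Reconcile Sections 2.4, 7.1, 9.2.1 and 9.2.2.1. If RR is primary for Part 2, as the primary endpoint entry in 2.4 states:

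- delete the statements in 7.1 and 9.2.2.1 that make all efficacy secondary;
- remove ORR for Part 2 from the secondary list in 2.4, keeping it for Part 1;
- place the RR analysis in 9.2.1 and relabel the response row of the overview table.

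**Denominator, whatever the label.** For Part 2 RR, replace both the set in the text of 9.2.2.1 and the open-ended entry in its table with one set: all treated Part 2 patients per indication, those without a post-baseline assessment counted as non-responders, with the exact 95% interval. Keep Per Protocol as a supportive analysis. In the missing-data column of that row, replace the reference to Section 11.3 with the non-responder rule. The plan does not itself require the all-treated set; it is recommended because it closes the gap for unscanned patients and leaves no choice of set.

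**Cost.** SAP wording only, with no new data. The headline RR may be slightly lower.

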## 7.2. Safety Endpoints

### 7.2.1. DLT Definitions

Severity of adverse events will be graded according to NCI CTCAE version 4.03. For the purpose of dose escalation, any of the following adverse events which are not considered related to disease progression, occurring in the first cycle of treatment (Q3W regimen: 21 days or until the patient receives the 2nd infusion if there are treatment delays, QW regimen: 21 days or until the patient receives the 4th infusion if there are treatment delays) will be classified as DLTs:

- Hematologic:
  - Grade 4 neutropenia lasting >7 days.
  - Febrile neutropenia (defined as neutropenia  $\geq$  Grade 3 and a single body temperature  $>38.3^{\circ}\text{C}$  or a sustained temperature of  $\geq 38^{\circ}\text{C}$  for more than one hour).
  - Grade  $\geq 3$  neutropenia with infection.
  - Any grade thrombocytopenia associated with clinically significant or life-threatening bleeding.
  - Grade 4 thrombocytopenia  $\geq 72$  hours or platelets  $\leq 10,000/\text{mm}^3$  regardless of duration.
- Non-hematologic:
  - Grade  $\geq 3$  toxicities, except those that have not been maximally treated (eg, nausea, vomiting, diarrhea).
  - Delay by more than 2 weeks in receiving the next scheduled cycle due to persisting toxicities attributable to PF-06647263.

Grade  $\geq 3$  cytokine release syndrome, infusion related reaction, allergic reaction, or anaphylaxis will not be considered as DLTs but may be a reason for study discontinuation and should be reviewed with Pfizer.

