### 2.1. Study Design

This is a Phase 1, two part, open label, multi-center, single arm, non-randomized, multiple dose, safety, pharmacokinetic and pharmacodynamic study of single agent ADC (PF-06647263) in sequential cohorts of adult patients with advanced solid tumors for whom no standard therapy is available. Successive cohorts of patients will receive doses of ADC (PF-06647263) intravenously on an outpatient basis every 21 days starting at a dose of 0.015 mg/kg.

The proposed doses, schedule(s) and PK timepoints may be reconsidered and amended during the study based on the emerging safety and pharmacokinetic data.

The actual number of patients enrolled will depend upon tolerability of ADC (PF-06647263) and the number of dose levels required to identify the MTD.

Patients will participate in the study for approximately 6 months. This assumes up to 4 weeks of screening, approximately 4 months of treatment, and a follow-up visit within 4 weeks after the last dose for adverse event (AE) and serious adverse event (SAE) collection. Treatment with study drug will continue until disease progression, patient refusal, unacceptable toxicity occurs, or the study is terminated.

This clinical study will include 2 parts. Part 1 will estimate the MTD in dose escalation cohorts in patients with advanced solid tumors for whom no standard therapy is available in order to establish the RP2D. Part 2 will include approximately 30 patients enrolled at the MTD in order to explore benefit from treatment as suggested by preclinical findings and will better define the safety profile at the RP2D. This expansion cohort will include approximately 15 patients with TNBC and 15 patients with OVCA. Additional safety information gathered in Part 2 may be used to modify the dose recommended for future Phase 2 trials.

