### 2.2. MTD Determination (Part 1)

A modified toxicity probability interval method (mTPI) targeting a DLT rate of 25% with an equivalence interval (20%-30%) will be utilized in order to estimate MTD. Patients will be enrolled in cohorts of 2 to 4, starting with 0.015 mg/kg for the first cohort. Subsequent dose levels may include a maximum 100% escalation until either the dose is  $\geq 0.060$  mg/kg, a patient experiences a DLT or Grade 2 thrombocytopenia considered related to PF-06647263

after which, dose escalation in subsequent cohorts will follow a modified Fibonacci scheme with maximum dose increases of 67%, 50%, 33%, 33%. Table 1 illustrates the possible dose levels when the Modified Fibonacci scheme is initiated at the 3rd dose level. Intermediate dose levels to further evaluate the safety and/or PK may be evaluated following discussion between Sponsor and Investigator.

	Modified Fibonacci^ scheme starts from dose level 3	Modified Fibonacci^ scheme starts from dose level 2	Modified Fibonacci^ scheme starts from dose level 1
Dose Level	Dose (mg/kg Q3W)	Dose (mg/kg Q3W)	Dose (mg/kg Q3W)
-1	0.01	0.01	0.01
1 (Starting dose)	0.015	0.015	0.015
2	0.030	0.030	0.025
3	0.060	0.050	0.038
4	0.100	0.075	0.050
5	0.150	0.100	0.067
6	0.200	0.134	0.089
7	0.267	0.178	0.119
8		0.238	0.158
9			0.211

The modified toxicity probability interval (mTPI) design uses a Bayesian decision-theoretic framework and a beta/binomial hierarchical model to tailor dose-escalation and de-escalation decisions. These rules are conceptually similar to those used by the 3+3 design and all the dose-escalation decisions for a given trial can be pre-calculated under the mTPI design and presented in a two-way table.

The decision rules to “dose escalate” (E), “no change in dose” (S), “dose de-escalate” (D) or “dose de-escalate, unacceptable toxicity” (U) are described below:

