**Table 1. Decision Rules**

Number	Number of Patients treated at a Dose level											
	DLT	n=2	n=3	n=4	n=5	n=6	n=7	n=8	n=9	n=10	n=11	n=12
0	E	E	E	E	E	E	E	E	E	E	E	E
1	D	S	S	S	E	E	E	E	E	E	E	E
2	U	D	D	S	S	S	S	S	S	S	S	S
3		U	U	D	D	S	S	S	S	S	S	S
4			U	U	U	D	D	D	D	D	D	S
5				U	U	U	U	U	D	D	D	D
6					U	U	U	U	U	U	U	D
7						U	U	U	U	U	U	U

Cohorts of patients could receive doses already tested but a dose that is associated with decision “Dose de-escalate, unacceptable toxicity” cannot be revisited and no more patients should be treated at this dose or higher doses for the remainder of the trial.

A minimum of 9 patients treated at the MTD dose is required to establish such dose as the RP2D. The maximum sample size would be N=70 but actual sample size will depend on the underlying dose toxicity profile and variability in actual data realization. The initial dosing regimen tested in Part 1 will be PF-06647263 administered once every 3 weeks (Q3W) consistent with the pre-clinical toxicity study. Evaluation of a weekly (QW) regimen will be initiated when the first patient treated with the Q3W regimen experiences a DLT or Grade 2 thrombocytopenia related to study treatment. The starting dose of the QW regimen will not exceed one-third of the highest Q3W dose evaluated. Once initiated, the 2 regimens will be evaluated in parallel and independently based on the same dose-escalation criteria as described above.

Dose escalation will stop under any of the following conditions:

1. The maximum sample size has been achieved;
2. At least 9 patients have been accumulated at a dose that is predicted to be the MTD;
3. All doses explored appear to be overly toxic and the MTD cannot be determined.

### 2.3. Part 2

Upon identification of the MTD, approximately 30 patients will be enrolled at the MTD in order to explore benefit from treatment as suggested by preclinical findings and will better define the safety profile at the RP2D. This expansion component aims at evaluating ADC (PF-06647263) at the MTD in two cancer indications:

- a. Previously treated metastatic TNBC which expresses EFNA-4 (15 patients).
- b. Advanced epithelial ovarian cancer, primary peritoneal or fallopian tube cancer (OVCA) which expresses EFNA-4 and which has progressed or relapsed during or within 6 months post most recent therapy with a platinum agent (15 patients).

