### **7.2.2. MTD Definition**

The MTD would be any doses with true toxicity probabilities in the Equivalence Interval (EI) where the EI is defined as [20%-30%].

In practice, the MTD will be the highest dose associated with the occurrence of DLTs  $\leq 33\%$  (eg, 3/9 evaluable patients experience a DLT during the first treatment cycle).

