### **7.2.3. Recommended Phase 2 Dose (RP2D) Definition**

The Recommended Phase 2 Dose (RP2D) is the dose chosen for further study based on Part 1 results. If the MTD proves to be clinically feasible for long term administration in a reasonable number of patients, such dose usually becomes the RP2D. Further experience with the MTD may result in a RP2D dose lower than the MTD.

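### The SAP 7.2.1 exemption for under-treated non-hematologic toxicities has no grade ceiling, so a Cycle 1 Grade 4 event can be left out of the DLT count

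*SAP*

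**What the plan says.** SAP 7.2.1 defines DLTs as listed Cycle 1 events not considered related to disease progression. There are two non-hematologic criteria. The first is Grade ≥3 "toxicities, except those that have not been maximally treated (eg, nausea, vomiting, diarrhea"). The second is "Delay by more than 2 weeks in receiving the next scheduled cycle due to persisting toxicities attributable to PF-06647263". A closing sentence separately removes Grade ≥3 cytokine release, infusion-related and allergic reactions; that sentence is outside this point.

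The DLT count is used in several places:
- **Dose decisions (2.2, Table 1).** Each pair of DLTs and patients maps to E (escalate), S (stay), D (de-escalate) or U (unacceptable toxicity). A U dose "cannot be revisited and no more patients should be treated at this dose or higher doses for the remainder of the trial".
- **Stopping and exclusion (4.2.1, Rules 1 and 2).** A dose is excluded when the posterior probability that its DLT rate exceeds 0.25 is above 0.975.
- **MTD (7.2.2).** "In practice, the MTD will be the highest dose associated with the occurrence of DLTs" at or below 33%, with 3/9 as the example.
- **Step size (2.2).** Steps of up to 100% end once the dose reaches 0.060 mg/kg or "a patient experiences a DLT or Grade 2 thrombocytopenia considered related to PF-06647263".
- **Weekly regimen (2.2).** Its evaluation "will be initiated when the first patient treated with the Q3W regimen experiences a DLT or Grade 2 thrombocytopenia related to study treatment".
- **Primary analysis (9.2.1).** DLT is the primary endpoint of the dose escalation part.

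**The concern.** The exception attaches to the whole Grade ≥3 class, so it reaches Grade 4 and, literally, Grade 5. The SAP does not define maximal treatment, and the example list is open. The hematologic bullets in the same section do set limits by grade, duration or platelet count.

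The delay criterion recovers only persistent toxicity. A Grade 4 event that settles without holding up the next cycle by more than 2 weeks escapes both criteria. A fatal event has no next cycle to delay.

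The error runs in one direction: an omitted event can only make a dose look safer. With 2 to 4 patients per cohort, one event often decides what dose the next patients receive.

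**Working it through.** **1. Is there an override?** I checked the other places where a severe event could be put back into the count.
- 2.2 and 4.2.1 use the DLT count as given.
- 6.8 deals with Cycle 1 dose deviations.
- 7.2.2 uses the DLT proportion.
- 7.2.6 and 9.2.3 report deaths and worst-grade adverse events, with Cycle 1 shown separately, but do not make them DLTs.
- 9.2.1 summarises DLTs as defined.

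None caps the exemption.

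**2. Reproducing Table 1.** Inputs from 2.2 and 4.2.1: target 0.25, intervals 0–0.20, 0.20–0.30 and 0.30–1, cut-off 0.975. The SAP gives no prior, so Beta(1,1) is assumed and the posterior is Beta(1+x, 1+n−x). Unit probability mass is interval probability divided by interval length.
- 0/3, Beta(1,4): 0.5904/0.2 = 2.95; 0.1695/0.1 = 1.70; 0.2401/0.7 = 0.34. Result: E.
- 1/3, Beta(2,3): 0.1808/0.2 = 0.90; 0.1675/0.1 = 1.68; 0.6517/0.7 = 0.93. Result: S.
- 1/2, Beta(2,2): 0.104/0.2 = 0.52; 0.112/0.1 = 1.12; 0.784/0.7 = 1.12. This is an exact tie between S and D, and the plan prints D.

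With that tie taken as D, the calculation agrees with every printed cell at n = 2 to 4.

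**3. Effect of one uncounted event.** Compare the printed decision at x DLTs with that at x−1.

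| n | x=1 | x=2 | x=3 | x=4 |
|---|---|---|---|---|
| 2 | D→E | U→D | – | – |
| 3 | S→E | D→S | U→D | – |
| 4 | S→E | D→S | U→D | U→U |

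There are 2+3+4 = 9 cells and 8 change, all towards less caution. Three of the 8 (2/2, 3/3, 3/4) lift a permanent exclusion. At n = 5 to 9 there are 5+6+7+7+7 = 32 cells (1 to 7 DLTs) and 15 change, three per column. That second count depends on reading the extracted rows from n = 2 rightwards, because they hold one cell more than the headings.

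**4. Rule 2**, Pr(p > 0.25), same assumed prior:
- 3/4, Beta(4,2): 0.984, above 0.975.
- 2/4, Beta(3,3): 0.896, below it.
- 4/9, Beta(5,6): 0.922; 3/9, Beta(4,7): 0.776. Neither excludes the dose.

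**5. MTD rule.** 4/9 = 44% is D and fails. 3/9 is S and is the plan's own passing example.

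**6. Triggers.** On the doubling schedule (0.015, 0.030, 0.060), 100% steps end at 0.060 anyway, so a missed first DLT affects step size only at 0.015 or 0.030. With one event in 3 patients at 0.015, the counted decision is to stay; uncounted, the next cohort may receive up to 0.030. The weekly-regimen trigger has no such dose limit. The only alternative trigger for either is related Grade 2 thrombocytopenia, which a Grade 4 diarrhea does not meet.

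**The case against.** **Intent.** The exemption concerns under-treated toxicity, and its examples are events that respond to supportive care. A reader might infer that the plan means to leave drug-related deaths out of the count. The wording permits that literally, but nothing shows it is intended. The realistic case is Grade 4.

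**Ownership.** A DLT definition is a clinical rule that normally sits in the protocol, and the SAP text may be copied from it. This does not remove the point, because the SAP restates the definition in full. It does mean that editing the SAP alone could make the two documents disagree.

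**Other safeguards.** A reader might infer that such an event would go unnoticed. It would not. SAP 9.2.3 tabulates Cycle 1 events by worst grade, and 7.2.6 includes deaths up to 28 days after the final dose. Doses and schedules "may be reconsidered and amended during the study based on the emerging safety and pharmacokinetic data", 100% is only a maximum step, intermediate doses are allowed, and "Further experience with the MTD may result in a RP2D dose lower than the MTD". These safeguards are real, but they are discretionary or descriptive, and none adds the event to the count.

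**Magnitude.** The 8 of 9 figure shows what any missed DLT would do. It weights likely and unlikely cells equally and says nothing about how often this clause causes a miss. Moving 4/9 to 3/9 needs three other counted DLTs at that dose. All of this stands.

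**Deliberate approach.** The infusion and allergic reaction sentence is also uncapped, so uncapped exemptions may be the sponsor's choice. That is possible, but those reactions are a named class referred for sponsor review. The clause at issue rests on an undefined judgement about treatment.

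**Conclusion.** The point holds on the text of 7.2.1. A Cycle 1 Grade 4 non-hematologic event, judged under-treated and causing no delay of more than 2 weeks, stays out of the Part 1 primary endpoint. If the patient has no other DLT, a cohort of 2, 3 or 4 with no other counted event goes to E instead of D, S and S respectively.

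The size is conditional on such an event occurring. The SAP gives no rate for one, and it is probably small. The Table 1 comparisons use the printed cells and need no prior; the Rule 2 probabilities assume Beta(1,1).

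Two stronger readings are not supported:
- A reader might compare columns of the dose table and conclude that a missed trigger makes the next dose 0.030 instead of 0.025 mg/kg. A counted DLT at 0.015 gives D at 1/2 and S at 1/3, so 0.025 is not the immediate alternative.
- A reader might multiply an event chance over the maximum of 70 patients. Any result would rest on a per-patient rate that the document does not supply.

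This is a worthwhile low-cost correction, not evidence that the escalation design fails.

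**What to change.** In the first non-hematologic bullet of 7.2.1, restrict the exception to Grade 3 toxicities and add: *Grade 4 and 5 toxicities count regardless of treatment.* Keep the open example list, since closing it would be a separate clinical change not argued here. Also keep the disease-progression limit and the infusion and allergic reaction sentence.

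Check the protocol's DLT definition and align it if it has the same wording. In 9.2.1, list by dose, beside the DLT table, the Cycle 1 events exempted under this bullet.

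The cost is one sentence and one short listing, plus possibly a protocol amendment. The downside is a possibly higher DLT rate and slightly more cautious escalation.
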